## 12.4 IOP

IOP (mmHg) in the study eye will be summarized at baseline using descriptive statistics.

IOP (mmHg) measured at 7-12 weeks after the first Ozurdex injection in the study eye, as well as at 7-12 weeks after each reinjection in the study eye, will be described using descriptive statistics. A figure will be presented for the mean IOP (mmHg) with 95% CIs at baseline, at each Ozurdex reinjection, and at 7-12 weeks after each Ozurdex injection in the study eye. In addition, the change in IOP (mmHg) from baseline to 7-12 weeks following each Ozurdex injection [DV], and the change from each Ozurdex reinjection to 7-12 weeks following reinjection [DV] will be described using descriptive statistics.

The following rules will apply for this description:

- IOP assessed on or after the day of subsequent injections (injection 2, injection 3, etc) will be included in this description.
- If there is more than one IOP measurement within the 7-12 week time window, the mean value will be considered for the description (See rule defined in section 21.2).
- If an Ozurdex injection is performed in the study eye at a follow-up visit, then investigators are asked to report in the EDC the IOP measured before the injection. This value will be considered for analysis.

## **13.0 PRIOR AND CONCOMITANT TREATMENTS AND SURGERIES**

Prior medication/surgery is defined as any medication/surgery taken before the date of the first Ozurdex injection in the study eye. Concomitant medication/surgery is defined as any medication/surgery taken on or after the date of the first injection in the study eye.

### **13.1 ANTI-VEGF AND CORTICOSTEROID TREATMENTS**

#### Prior medications

Prior treatments with anti-VEGF and corticosteroids in the study eye will be summarized using descriptive statistics for the following parameters: any anti-VEGF or corticosteroids treatment (Yes, No), at least one anti-VEGF treatment (Yes, No) [DV] and number of treatments [DV], at least one corticosteroid (Yes, No) [DV] and number of treatments [DV]. Then, each anti-VEGF treatment pre-listed in the eCRF (Avastin®, Lucentis®, Eylea® and Macugen®) and each corticosteroid treatment pre-listed (Triamcinolone®, Iluvien®) will be summarized by the number and percentage of patients treated and the number of treatments received per patient. The number and percentage of patients treated with at least one treatment of the category 'Other anti-VEGF therapy' will be described and treatments reported within this category will be described by generic name (WhoDrug B3 format version 01SEP2018). The same will be done for treatments reported in the category 'Other corticosteroid therapy'.

The time from the last anti-VEGF treatment to baseline (months) [DV], the time from the last corticosteroid treatment to baseline (months) [DV] and the time from the last treatment (the last among anti-VEGF and corticosteroids) to baseline (months) [DV] will be described using descriptive statistics.

#### Concomitant medications

Concomitant anti-VEGF and corticosteroid treatments will be summarized using the same methodology as for prior medications (see above) except for times from last treatment to baseline that are not applicable for concomitant treatments. The time from baseline to first anti-VEGF treatment (months) [DV] and time from baseline to first corticosteroid treatment (months) [DV] will be described using descriptive statistics, as well as the time from each Ozurdex reinjection to first receipt of anti-VEGF treatment (months) [DV] and corticosteroids treatment (months) [DV], respectively.

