## 13.4 CATARACT AND GLAUCOMA PROCEDURES IN THE STUDY EYE

### Prior procedures

Ocular surgical history and treatment history in the study eye prior to the first Ozurdex injection on the study eye will be summarized using descriptive statistics for the following parameters:

- Glaucoma related interventions: glaucoma laser (Yes, No), trabeculectomy (Yes, No), glaucoma valve implant (Yes, No) and laser peripheral iridotomy (Yes, No)
- Retinal lasers: focal retinal laser (Yes, No), PRP retinal laser (Yes, No). The number of treatments per patient and the time from the last treatment to baseline (months) [DV] will also be summarized for focal and PRP retinal laser separately.
- Retinal surgeries: pars plana vitrectomy (Yes, No) and, if yes, description of the number of treatments per patient and of the time from the last treatment to baseline (months) [DV].
- Other treatments/interventions: any treatment (Yes, No) and description of treatments reported by PT (MedDRA version 21.1). If several treatments with the same PT are reported for the same patient, the patient will be counted once for that PT.

Concomitant procedures

Any concomitant ocular surgeries in the study eye (Yes, No), cataract surgery, each glaucoma intervention (Glaucoma surgery, glaucoma laser, trabeculectomy, glaucoma valve implant, laser peripheral iridotomy) and retinal related surgery (pars plana vitrectomy) will be summarized using descriptive statistics. Time from baseline to first surgical procedure (months) [DV] will be presented for each procedure.

Retinal related laser procedures (focal retinal laser; PRP retinal laser) will be summarized as above; however, these laser procedures also will be described by intervals after each Ozurdex reinjection during follow-up. Specifically, time from each Ozurdex reinjection to the first retinal laser procedure (months) will be summarized in addition to time from baseline to retinal laser procedure (months) [DV].

Other procedures reported in the 'Other' category will be summarized by PT (MedDRA version 21.1). If several procedures/treatments with the same PT are reported for the same patient, the patient will be counted once for that PT.

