## **19.0 DETERMINATION OF SAMPLE SIZE**

The study aims to select 150 patients. As study primary objective is to assess reinjection interval of Ozurdex implant in real-world, sample size calculations were performed to evaluate the precision around the mean of the reinjection interval.

Few data were published on the reinjection interval in patients diagnosed with DME in real-world. Matropasqua et al. reported a mean  $\pm$  standard deviation (SD) of  $6.7 \pm 2.3$  months in 27 Italian patients. Querques et al. reported a mean of 4.9 and 4.7 months from respectively 570 French patients of a pharmacist database and 114 patients from the French Social Security database (no standard deviations were available). The same study also reported a mean ( $\pm$ SD) of  $4.8 \pm 1.8$  months between reinjections based on data from 111 French ophthalmologists who completed a survey about their practice.

The precision of the 95% CI of the mean ( $\omega$ , half of the width of the CI) is determined using the following formula:

$$\omega = \frac{1.96 \times SD}{\sqrt{n}}, \text{ where SD is the standard deviation and } n \text{ is the sample size.}$$

Table 18-1 shows the precision and 95% CI of the mean considering a SD ranging from 1.5 to 3.0 and a sample size of 150 patients.

**Table 18-1 Precision ( $\omega$ ) and 95% CI of the mean considering a standard deviation ranging from 1.5 to 3.0, a mean ranging from 4.7 to 6.7 and a sample size of 150 patients**

SD	Mean (months)				
	$\omega$	4.7	5.5	6.0	6.7
1.5	0.2	4.5-4.9	5.3-5.7	5.8-6.2	6.5-6.9
2.0	0.3	4.4-5.0	5.2-5.8	5.7-6.3	6.4-7.0
2.5	0.4	4.3-5.1	5.1-5.9	5.6-6.4	6.3-7.1
3.0	0.5	4.2-5.2	5.0-6.0	5.5-6.5	6.2-7.2

Considering SD of the mean reinjection interval ranging from 1.5 to 3 months, the selection of 150 patients will enable the description of a mean reinjection interval with precision ranging from 0.2 to 0.5 months, i.e. from 6 to 15 days (worst case).

For example, for a mean interval between two Ozurdex injections of 6.0 months, the 95% CI of the mean would be 6.0 [5.5-6.5] months in the worst case (i.e., 183 days [168-198],  $\omega = 15$  days).

A secondary objective of the study is to assess drug effectiveness in a subgroup of patients who are naïve of any anti-VEGF treatment. One of the outcomes of interest for this subgroup of patients will be the change in BCVA from the first injection to 7-12 weeks following each reinjection.

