## **21.0 DATA HANDLING CONVENTIONS**

### **21.1 STATISTICAL RULES AND DATA FORMATS**

#### Continuous variables

Continuous (quantitative) variables will be described by the number of non-missing and missing observations, mean, SD, median, first and third quartiles and extreme values (minimum and maximum). The following rules will be applied:

- If the raw/derived variable is an integer, then mean, median, SD, first and third quartiles will be rounded to one decimal.
- If the raw/derived variable is a decimal number, then mean, median, SD, first and third quartiles will be reported using the same number of decimal places as the raw/derived data.
- Minimums and maximums will be reported with the same number of decimals with which the raw/derived variable is recorded/calculated.
- If the standard deviation is not computable, then it will be displayed as 'NA' (Not applicable).

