### Follow-up period

The period starting the day after the day of the first Ozurdex injection in the study eye is the follow-up period (= post-baseline period). End of follow-up occurs at the last study visit or first receipt of concomitant treatment with anti-VEGF and/or corticosteroids, whichever comes first.

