### **21.3 DERIVED VARIABLES**

Derivation details of all variables that will be derived in analysis datasets are defined in this section. Derived variables are identified in square brackets ([DV]) in the other sections of the SAP.

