### Time from the last Ozurdex injection (before or the day of AESI) to AESI

The time will be derived in days as:

Onset date of AESI – Date of the last Ozurdex injection. The last Ozurdex injection will be identified as the last injection among those performed on or before the onset date of the AESI.

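### Times from each reinjection to add-on treatment are summarised in treated eyes only and have no derivation, so they shorten with reinjection number even at constant risk, and one event can be credited to several implants

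*SAP*

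**What the plan says.** SAP 13.1 (Concomitant medications) summarises the "time from each Ozurdex reinjection to first receipt of anti-VEGF treatment" and the corresponding time to a corticosteroid. SAP 13.2 has the same variable for IOP-lowering medication. SAP 13.4 states that "time from each Ozurdex reinjection to the first retinal laser procedure (months) will be summarized", introduced by the remark that "these laser procedures also will be described by intervals after each Ozurdex reinjection during follow-up".

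The summary method is in SAP 21.1: "Continuous (quantitative) variables will be described by the number of non-missing and missing observations, mean, SD, median, first and third quartiles". Missing values are counted but do not enter the mean or quartiles, and nothing is censored.

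The reinjection times in 13.1 and 13.2 are marked as derived variables. SAP 21.3 promises that "Derivation details of all variables that will be derived in analysis datasets are defined in this section". However, 21.3.4 covers only study duration, age, time to baseline, AESI duration and time from the last injection to an AESI. No rule says when the clock for add-on treatment stops, or what value an untreated eye receives.

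Two other rules bear on the point. SAP 21.2 says "End of follow-up occurs at the last study visit or first receipt of concomitant treatment with anti-VEGF and/or corticosteroids, whichever comes first". For AESIs, 21.3.4 does tie the event to one injection: "The last Ozurdex injection will be identified as the last injection among those performed on or before the onset date of the AESI".

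**The concern.** There are two separate problems.

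The first is the treated-only summary. A time to first treatment exists only if the treatment occurred before the records end. Later reinjections have less record left, so only short times can be observed after them. Laid out by reinjection number, the table will tend to show add-on treatment coming sooner after each further implant, whether or not that is so.

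The second is attribution. With no stop at the next reinjection, a single anti-VEGF injection or laser supplies a value to the row of every earlier reinjection, including implants that were replaced long before the event.

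At stake is how a reader interprets the concomitant-treatment tables. Receipt of concomitant DME treatment in the study eye is part of the minimum required dataset (Protocol 8.2.4), so these tables are likely to be read.

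**Working it through.** The documents give no figure for this variable, so there is none to reproduce.

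**Inputs from the documents.** The mean reinjection interval is 4.7 to 6.7 months (SAP 19.0: "a mean ranging from 4.7 to 6.7 and a sample size of 150 patients"). SDs of 1.8 and 2.3 months are also in SAP 19.0. Follow-up is at least 12 months (SAP 4.0) and at most 44 months, from 1 January 2015 to 1 September 2018.

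**Assumptions.** The add-on rate is constant. It is not in the documents, so a range is used. Follow-up is uniform over 12–44 months.

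**Step 1: one event, several values.** Take reinjections at months 6, 12 and 18 and a first anti-VEGF at month 20. The literal times are 20 − 6 = 14, 20 − 12 = 8 and 20 − 18 = 2 months. Only the 2 months belongs to the implant that the event followed.

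**Step 2: why the treated-only mean falls.** With constant rate λ and remaining follow-up R, the mean time among those treated is

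1/λ − R / (exp(λR) − 1).

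Take λ = 0.3/12 = 0.025 per month, records ending at month 30, and reinjections at months 6, 12, 18 and 24, so R = 24, 18, 12 and 6:

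- R = 24: 40 − 24/0.8221 = 10.8 months
- R = 18: 40 − 18/0.5683 = 8.3 months
- R = 12: 40 − 12/0.3499 = 5.7 months
- R = 6: 40 − 6/0.1618 = 2.9 months

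The true mean is 40 months every time. The formula contains remaining follow-up and not the date of the next reinjection.

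**Step 3: across patients.** Each scenario simulated 150,000 patients with patient-specific intervals and the text applied literally. Mean months by reinjection number:

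| Interval, mean ± SD | Assumed rate/year | 1 | 2 | 3 | 4 | 5 |
|---|---|---|---|---|---|---|
| 4.7 ± 1.8 | 0.1 | 12.8 | 11.3 | 10.0 | 9.0 | 8.2 |
| 4.7 ± 1.8 | 0.3 | 11.6 | 10.3 | 9.3 | 8.4 | 7.7 |
| 4.7 ± 1.8 | 1.0 | 8.1 | 7.5 | 7.0 | 6.5 | 6.2 |
| 6.7 ± 2.3 | 0.1 | 12.3 | 10.3 | 8.8 | 7.8 | 6.9 |
| 6.7 ± 2.3 | 0.3 | 11.0 | 9.4 | 8.2 | 7.3 | 6.6 |
| 6.7 ± 2.3 | 1.0 | 7.8 | 7.0 | 6.4 | 6.0 | 5.6 |

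The fall is gentler than in Step 2 because eyes that reach later reinjections tend to have longer follow-up or shorter intervals. If intervals are instead drawn independently within a patient, with rates of 0.05 to 1.0 per year, the mean falls from about 8–13 months after reinjection 1 to about 5–8.5 months after reinjection 4.

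**Step 4: separating the two problems.**

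- No stop, but untreated eyes kept as censored (assumed 0.15 per year, 5.5-month intervals): the event rates after reinjections 1 to 4 are 0.150, 0.149, 0.149 and 0.147 per year. The trend is gone.
- Stop at the next reinjection, treated eyes only (0.3 per year): the mean still falls over reinjections 1 to 5, from 2.6 to 1.9 months (4.7-month intervals) and from 3.4 to 2.2 months (6.7-month intervals).
- Stop and censoring together (0.3 per year): the rates are 0.298, 0.296, 0.297, 0.299, 0.304 and 0.299, 0.303, 0.298, 0.305, 0.303 per year. They are flat, and each event counts once.

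**Step 5: size of the misattribution.** This is the share of eyes credited with an event after reinjection 1, without a stop against before the next reinjection:

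- 0.3 per year, 4.7 months: 56,707/133,366 = 42.5% against 14,370/133,366 = 10.8%
- 0.3 per year, 6.7 months: 50,733/126,881 = 40.0% against 18,246/126,881 = 14.4%
- 0.1 per year, 4.7 months: 25,157/144,246 = 17.4% against 5,514/144,246 = 3.8%
- 0.1 per year, 6.7 months: 22,710/141,652 = 16.0% against 7,109/141,652 = 5.0%

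Over reinjections 1 to 5, each event supplies 1.9 to 3.1 values across the six scenarios in the table.

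**The case against.** **The missing stop does not cause the shortening.** A reader might infer that it does, because within one patient the times fall by exactly one interval each. Step 4 shows otherwise: the trend across patients disappears once untreated eyes are retained, with or without a stop. Time from a given reinjection to the next add-on treatment, however many implants intervene, is a legitimate quantity, and one event appearing in several rows is inherent in it. This stands. The missing stop is a question of attribution only.

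**The SAP is silent rather than wrong.** A reader might infer that it instructs the clock to run past the next reinjection. It does not say so. For laser, the phrase about intervals after each reinjection could be read as bounded, although the sentence that follows it sets no bound. A programmer could borrow the AESI rule, and the table specifications are in a separate document. This stands in part: what the documents show is a missing derivation, and the literal wording gives the unbounded version.

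**The end-of-follow-up rule helps.** Under 21.2, reinjections after the first anti-VEGF or corticosteroid fall outside follow-up. That does not prevent the first event being timed from every reinjection before it, nor does it bring untreated eyes into the mean.

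**Low consequence.** The variables feed no analysis in SAP 15, the number missing will be displayed, and SAP 4.0 disclaims causal conclusions. All true, and it sets the weight of the point. A count of missing values does not remove the trend.

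**Conclusion.** The point holds as a minor improvement to descriptive tables. The literal plan gives treated-only means that decline with reinjection number under constant risk, because follow-up is limited. The direction was the same in every scenario tried. The size depends on an add-on rate that the documents do not give: for 0.05 to 1.0 per year, about 8–13 months after reinjection 1 falls to about 5–9 months after reinjection 4, taking both interval models together. The upper end, about a year after reinjection 1, applies at low rates; at 1.0 per year it is about 8 months. The missing stop separately credits events to implants they did not directly follow.

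It would be too strong to conclude that the reinjection-interval results are affected. The interval in SAP 15.1 is computed from injection dates and does not use these variables.

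**What to change.** Add one derivation to SAP 21.3.4, and refer to it from 13.1, 13.2 and 13.4:

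1. Assign each anti-VEGF, corticosteroid, IOP-lowering drug or retinal laser to the last Ozurdex injection in the study eye on or before its date, as is already done for AESIs.
2. For each reinjection, report the number at risk and the number and percentage treated before the next reinjection or last visit.
3. Replace the treated-only mean and median by a Kaplan-Meier or cumulative incidence estimate that keeps untreated eyes as censored. Both this and item 1 are needed, since a stop alone leaves the falling mean.
4. State whether an eye whose first treatment came before a given reinjection counts as at risk for that reinjection. The present text leaves open whether its time is negative, missing or taken to the next treatment.

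The cost is short wording in three sections, one derivation and a standard procedure call. The downside is that reinjection may be related to the need for add-on treatment: SAP 15.2.2 lists disease progression and lack of effect among the reasons for reinjection. Simple censoring at reinjection may therefore be informative. Either treat reinjection as a competing event or state the caveat beside the estimate.

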## 13.2 CONCOMITANT IOP-LOWERING MEDICATIONS

Concomitant IOP-lowering medications in the study eye will be summarized using descriptive statistics for the following parameters: at least one IOP-lowering medication (Yes, No) [DV] and description of IOP-lowering medication by generic name (WhoDrug B3 format version 01SEP2018). The time from baseline to first IOP-lowering medication (months) [DV] and time from each Ozurdex reinjection to first receipt of IOP-lowering medication (months) [DV] will be described using descriptive statistics.

## 13.3 OTHER CONCOMITANT OPHTHALMIC MEDICATIONS

Concomitant ophthalmic medications other than anti-VEGF, corticosteroids and IOP-lowering medications will be summarized using descriptive statistics for the following parameters: at least one other medication in the study eye (Yes, No) [DV], at least one other systemic medication (Yes, No) [DV]. Medications will be described by generic name (WhoDrug B3 format version 01SEP2018) separately for medications in the study eye and medications for other medical conditions.

## 13.4 CATARACT AND GLAUCOMA PROCEDURES IN THE STUDY EYE

### Prior procedures

Ocular surgical history and treatment history in the study eye prior to the first Ozurdex injection on the study eye will be summarized using descriptive statistics for the following parameters:

- Glaucoma related interventions: glaucoma laser (Yes, No), trabeculectomy (Yes, No), glaucoma valve implant (Yes, No) and laser peripheral iridotomy (Yes, No)
- Retinal lasers: focal retinal laser (Yes, No), PRP retinal laser (Yes, No). The number of treatments per patient and the time from the last treatment to baseline (months) [DV] will also be summarized for focal and PRP retinal laser separately.
- Retinal surgeries: pars plana vitrectomy (Yes, No) and, if yes, description of the number of treatments per patient and of the time from the last treatment to baseline (months) [DV].
- Other treatments/interventions: any treatment (Yes, No) and description of treatments reported by PT (MedDRA version 21.1). If several treatments with the same PT are reported for the same patient, the patient will be counted once for that PT.

Concomitant procedures

Any concomitant ocular surgeries in the study eye (Yes, No), cataract surgery, each glaucoma intervention (Glaucoma surgery, glaucoma laser, trabeculectomy, glaucoma valve implant, laser peripheral iridotomy) and retinal related surgery (pars plana vitrectomy) will be summarized using descriptive statistics. Time from baseline to first surgical procedure (months) [DV] will be presented for each procedure.

Retinal related laser procedures (focal retinal laser; PRP retinal laser) will be summarized as above; however, these laser procedures also will be described by intervals after each Ozurdex reinjection during follow-up. Specifically, time from each Ozurdex reinjection to the first retinal laser procedure (months) will be summarized in addition to time from baseline to retinal laser procedure (months) [DV].

Other procedures reported in the 'Other' category will be summarized by PT (MedDRA version 21.1). If several procedures/treatments with the same PT are reported for the same patient, the patient will be counted once for that PT.

**14.0 EXTENT OF EXPOSURE**

The description of Ozurdex implant injections received by patients (number and reinjection interval) is covered in Section 15.1.

## **15.0 ANALYSES OF THE OBJECTIVES OF THE STUDY**

### **15.1 ANALYSIS OF THE PRIMARY OBJECTIVE**

The primary objective '*To assess reinjection interval of Ozurdex implants in patients with DME in real-world in Germany and Switzerland*' will be assessed by the following outcomes:

- Total number of Ozurdex reinjections in the study eye during follow-up, and considering years after the first Ozurdex injection in the study eye (See definition in Table 21-1).
- Re[injection interval defined in months as: (Date of injection (j+1) – Date of injection j) ÷ (365.25÷12), for j=1,...,n where n is the number of reinjections in the study eye. The result will be rounded to 0.1.

The number of Ozurdex reinjections in the study eye per year will be first summarized using descriptive statistics for the following parameters:

- The total number and percentage of Ozurdex reinjections received during follow-up.
- Number and percentage (with 95% CI) of patients with at least one Ozurdex reinjection during Year 1 (See definition in Table 21-1), and number of reinjections per patient during Year 1, for all patients in the analysis population. Note: the first Ozurdex injection will not be considered here, only reinjections will be counted.
- Number and percentage (with 95% CI) of patients with at least one Ozurdex reinjection and number of reinjections per patient during Year k (k=2, 3), for patients having a complete Year k of follow-up (see definition of 'Complete year' in Section 21.2).
- Number and percentage of patients receiving each Ozurdex reinjection (first, second, third, etc) for each year of follow-up (Year k, k=1 to 3) considering patients having the complete year of follow-up.

The Ozurdex reinjection interval in the study eye will be described using descriptive statistics for the following parameters:

- Re[injection interval (months) considering all eligible reinjections recorded in the EDC. The 95% CI of the mean will also be presented.
- Re[injection interval (months) considering each reinjection separately (i.e. first reinjection, second reinjection, etc). 95% CI of the mean will also be presented.

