#### 8.2.1 Inclusion Criteria

A patient must meet **all** of the following criteria to be eligible for participation in the study.

1. Patient received at least two Ozurdex implants in the study eye to treat visual impairment due to DME
2. Male or female patient aged  $\geq 18$  years at time of first Ozurdex implant injection
3. First Ozurdex implant injection occurred after 1 January 2015
4. Patient was followed-up at the site for at least 12 months after the first Ozurdex implant in the study eye

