### **14.2.2.2 Primary Objective**

Number of patients with at least one reinjection and number of reinjections per patient during the year following the first Ozurdex implant injection will be summarized descriptively for all patients from the Analysis population. For patients with more than one year of follow-up, number of patients with at least one reinjection and number of reinjections per patient during the follow-up year considered will be described for each year of follow-up (e.g. 2nd year of follow-up, 3rd year of follow-up...). The number and percentage of patients receiving each injection (first, second, etc.) will be presented for each year of follow-up.

Time between Ozurdex implant injections will be summarized overall and for each reinjection, i.e. first reinjection, second reinjection...

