**Table 21-1 Definition of years after the first Ozurdex injection in the Study eye**

Year # [a]	Year definition [b]
Year 1	Days [2, 365]
Year 2	Days [366, 731]
Year 3	Days [732, 1096]

---

- [a] As per protocol all patients will have at least 1 complete year of follow-up at the site and the maximum number of complete years will be 3. The 1st Ozurdex injection should occur after 1 January 2015 and data will be collected up to 1 September 2018.
- [b] Relative to the date of the first Ozurdex injection in the study eye. Day 1 = the date of the first Ozurdex injection in the study eye. There is no Day 0.

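### The pooled mean of completed reinjection intervals is biased short, through over-weighting of frequently injected patients and loss of open intervals, and the by-reinjection means fall without any true change

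*SAP*

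**What the plan says.** SAP 15.1 defines the interval as the date of injection j+1 minus the date of injection j, in months, for j = 1 to n, "where n is the number of reinjections in the study eye". The time from the last implant to the end of observation is therefore not an interval. Two summaries follow, each with a 95% CI of the mean: the "interval (months) considering all eligible reinjections recorded in the EDC", and the same for each reinjection number separately. Protocol 14.2.2.2 plans the same: "Time between Ozurdex implant injections will be summarized overall and for each reinjection".

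Neither document has a censoring rule or a time-to-event analysis of the interval. SAP 21.4 covers partial dates only. The bias sections (Protocol 7.3, SAP 7.0) do not mention the matter.

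Inclusion (Protocol 8.2.1) requires that "Patient received at least two Ozurdex implants in the study eye to treat visual impairment due to DME" and that "Patient was followed-up at the site for at least 12 months after the first Ozurdex implant in the study eye". First implants run from 1 January 2015 to 1 September 2017 and data stop on 1 September 2018 (Protocol 9.2), so calendar follow-up ranges from 12 to 44 months.

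**The concern.** The reinjection interval is the primary objective, and Protocol 8.2 expects the results to generalise to patients with DME treated with Ozurdex in the two countries. Two features of the pooled mean pull it below the typical patient's interval.

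- **Weighting.** A patient injected every 4 months adds about twice as many intervals over the same period as one injected every 8 months.
- **Open intervals.** A long interval is more likely than a short one to be unfinished when observation ends, and unfinished intervals are dropped.

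In the by-reinjection table, the later rows hold mainly patients who reinject quickly, and within each row the long intervals are cut off. A reader could take the falling means for a change with repeated use. Enrolling more patients removes neither effect; it only narrows the CI around the shifted value.

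**Working it through.** **1. The plan's own figure.** Half-width = 1.96 × SD / √150 (SAP 19.0).

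- SD 1.5, 2.0, 2.5 and 3.0 give 0.240, 0.320, 0.400 and 0.480 month. The stated 0.2 to 0.5 is reproduced.
- SD 2.3 gives 0.37 month.

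**2. Simulation inputs.**

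- From the documents: mean 4.7 to 6.7 and SD 1.5 to 3.0 (SAP 19.0), follow-up 12 to 44 months, and at least one completed interval.
- Assumed: interval shape (gamma or lognormal), share of variance between patients, distribution of follow-up within its range, and a true interval that does not change with reinjection number.

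**3. Pooled error.**

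- Over the planning range, with lognormal intervals, the pooled mean is too short by about 0.1 to 0.5 month if intervals are independent within patient. It is too short by about 0.2 to 1.1 months if half the variance is between patients.
- At mean 6.0, SD 2.3 and uniform follow-up, the pooled mean is 5.79 (independent) or 5.43 (half between). The errors are 0.21 and 0.57, against a half-width of 0.37.

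**4. How much is weighting.** Take gamma intervals, mean 6.0, SD 2.5 and half the variance between patients.

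- With 12 to 44 months of follow-up the pooled mean is 5.31. With 200 to 300 months, where almost nothing is open, it is still 5.48.
- Share due to weighting: (6.0 − 5.48) / (6.0 − 5.31) = 0.52 / 0.69, about three quarters.
- Closed-form check: with very long follow-up the pooled mean tends to 1 / E(1/μ), where μ is a patient's own mean interval. For gamma-distributed μ with mean m and variance v this equals m − v/m. Here v = 0.5 × 2.5² = 3.125, so 6.0 − 3.125/6.0 = 5.48.

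**5. By reinjection number** (lognormal, mean 6.0, SD 2.3, uniform 12 to 44 months; Kaplan-Meier means restricted at 24 months):

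| Reinjection | 1 | 2 | 3 | 4 | 5 |
|---|---|---|---|---|---|
| Completed only, independent | 6.00 | 5.90 | 5.78 | 5.73 | 5.64 |
| Kaplan-Meier mean, independent | 6.00 | 6.00 | 5.98 | 6.00 | 6.03 |
| Completed only, half between | 5.99 | 5.84 | 5.61 | 5.36 | 5.05 |
| Kaplan-Meier mean, half between | 5.99 | 5.96 | 5.82 | 5.61 | 5.38 |
| Open, % of those at risk | 0 | 4–5 | 16 | 22–23 | 28–30 |

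Censoring removes the false decline when intervals are independent. It only reduces the decline when patients differ. In the gamma case of step 4, Kaplan-Meier medians still fall from 5.60 at the first reinjection to 4.68 at the sixth.

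**6. One value per patient.** The first interval is complete for everyone by inclusion criterion 1; its simulated mean is 5.94 to 6.03 when the truth is 6.0. The mean of per-patient means is 5.95 to 6.01. The agreement is expected. If a patient's intervals are exchangeable, the event that exactly n of them were completed treats those n alike, so their average has the same expectation as the first.

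**The case against.** The strongest objections, and what stands of each:

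- **The size is not in the documents.** This stands. Neither the between-patient share nor the follow-up mix is given. Three of the four published means cited for planning are 4.7 to 4.9 months. At means of 4.7 to 4.8 with little or no between-patient variance, the error is only 0.09 to 0.15 month, below the matching half-widths of 0.24 (SD 1.5) and 0.29 (SD 1.8).
- **Sites select the earliest index dates first (Protocol 9.2), so follow-up will be long.** This stands in part. With 30 to 44 months (mean 6.0, SD 2.5, half between), the first three by-reinjection means are nearly clean (5.99, 5.98, 5.92). The fall then moves to the fourth to sixth (5.64, 5.22, 4.75), and the pooled mean is still only about 5.36.
- **Much is already planned.** This stands. The first-reinjection interval is reported with a CI, SAP 21.1 provides medians and quartiles, and neither document names the pooled mean as the headline. The per-year counts, the other primary outcome, are restricted to complete years for Years 2 and 3 and are not biased in this way. But no such guard applies to the interval, and the planned medians use the same completed intervals.
- **The study is descriptive, with no hypothesis.** True, but a description still needs a stated target, and a per-injection mean differs from a per-patient mean.

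A reader might infer that the data cut-off alone shortens the mean and that Kaplan-Meier would cure it. Neither follows: when patients differ, weighting is the larger part, and a by-reinjection decline survives censoring.

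**Conclusion.** The plan should be changed, but the point does not invalidate the study. The direction is firm: with a constant true interval and 12 to 44 months of follow-up, the pooled completed-interval mean was too short and the by-reinjection means fell in every scenario run. The size is conditional: about 0.1 to 0.5 month under independence, where it is mostly below the planned half-width, and about 0.2 to 1.1 months with half the variance between patients, where it can exceed it.

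Three limits apply. A real lengthening of intervals could mask the artefact. The simulations assume that every patient would eventually be reinjected, whereas an open gap may mean that treatment was stopped or switched. And all summaries describe patients reinjected at least once. Long first intervals are lost through selection rather than censoring. This affects 0 to about 1% of patients with 12 to 44 months of follow-up and up to about 5 to 6% at exactly 12 months, and the analysed sample cannot repair it.

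**What to change.** In SAP 15.1:

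1. Make the headline a one-value-per-patient summary: the first reinjection interval, together with the mean of per-patient mean intervals. Describe both as applying to patients reinjected at least once.
2. For each later reinjection, report the Kaplan-Meier median and quartiles of time from implant j to implant j+1, with numbers at risk, among all patients who received implant j. Censor open intervals. State whether censoring is at the last visit or at the SAP 21.2 end of follow-up, which can fall earlier, at the first concomitant anti-VEGF or corticosteroid. Show the other as a sensitivity analysis, and note that censoring at a treatment switch may be informative. Define which reinjections count as eligible on the same basis, since the SAP does not.
3. Keep the pooled completed-interval mean as supportive, labelled as per injection and excluding open intervals. State that neither the by-reinjection means nor the Kaplan-Meier results may be read as a within-patient trend.

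The cost is SAP wording and a few extra tables; injection and visit dates are already collected. The headline interval will probably be somewhat longer than the pooled one.
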